Withdrawal of consent is a critical trial event and therefore should be approached with the same degree of importance and care as is used in initially obtaining informed consent. The reasons for a subject's intended withdrawal need to be completely understood, documented, and managed to protect the rights of the subject and the integrity of the trial. A subject may initially express their desire to interrupt or discontinue IMP administration, which is not equivalent to a complete withdrawal of consent for further participation (see [Section 3.8.3.1](#) and [Section 3.8.3.2](#)). A subject may, however, indicate that further trial participation is creating a burden on their work or social schedule. Therefore, the investigator should follow the procedures outlined in [Section 3.8.3.3](#) to determine if the subject can continue participation in the trial if modifications to his/her treatment and/or schedule of assessments can be accommodated. Only subjects who withdraw their permission for all of the above degrees of follow-up are considered to have completely withdrawn their consent to participate in the trial.

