7.6.1.2 Double-blind Randomized Withdrawal Phase

The incidence of the following events during randomized withdrawal phase will be summarized for the Randomized Safety Sample:

- TEAEs
- TEAEs by severity
- TEAEs potentially causally related to the IMP
- TEAEs with an outcome of death
- Serious TEAEs
- TEAEs leading to discontinuation of the IMP

The above summaries will also be prepared for TEAEs potentially causally related to the IMP.

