9.2 Adverse Events

All adverse events (AEs) are coded by system organ class and Medical Dictionary for Regulatory Activities (MedDRA) preferred term (Version 23.0 or later). A treatment-emergent AE (TEAE) is defined as an AE which starts after start of trial medication (Aripiprazole IM depot/Oral tablets), or an AE continues from baseline of the specific phase and becomes serious, trial drug-related or results in death, discontinuation, interruption or reduction of study medication during this phase. The incidences of the following treatment-emergent adverse events (TEAEs) will be summarized by treatment group for the safety samples:

- TEAEs by severity
- Potentially drug related TEAEs
- TEAEs with an outcome of death
- Serious TEAEs
- Discontinuations due to TEAEs
- Death
- Non- Serious TEAEs

Deaths, SAEs, and AEs leading to discontinuation from the trial will be listed for the safety samples.

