- CT-5.5.2 Clinical Global Impressions Scale for Tourette's Syndrome (CGI-TS) Improvement Score - Mean by Week - OC (ITT Sample)
- CT-6.1.1 Simpson-Angus Scale Total Score - Mean Change from Baseline by Week - OC (Randomized Safety Sample)
- CT-6.1.2 Barnes Akathisia Rating Scale Global Score - Mean Change from Baseline by Week - OC (Randomized Safety Sample)
- CT-6.1.3 AIMS Movement Rating Score - Mean Change from Baseline by Week - OC (Randomized Safety Sample)
- CT-6.2.1 Columbia-Suicide Severity Rating Scale (C-SSRS) (children's version) - Suicidality (Randomized Safety Sample)
- CT-6.2.2 Columbia-Suicide Severity Rating Scale (C-SSRS) (children's version) by Type (Randomized Safety Sample)
- CT-7 Extent of Exposure to Investigational Medicinal Products Double-Blind Randomized Withdrawal Phase (Randomized Safety Sample)
- CT-8.1 Adverse Events (All Causalities) (Randomized Safety Sample)

- CT-8.2.1 Incidence of Treatment-Emergent Adverse Events by System Organ Class and MedDRA Preferred Term (Randomized Safety Sample)
- CT-8.2.2 Incidence of Treatment-Emergent Adverse Events by System Organ Class, MedDRA Preferred Term and Severity (Randomized Safety Sample)
- CT-8.2.3 Incidence and Occurrence (Number of Events) of non-Serious Treatment-emergent Adverse by System Organ Class and MedDRA Preferred Term (Randomized Safety Sample)
- CT-8.3.1 Incidence and Occurrence (Number of Events) of Potentially Drug-Related Treatment-Emergent Adverse Events by System Organ Class and MedDRA Preferred (Randomized Safety Sample)
- CT-8.3.2 Incidence of Potentially Drug-related Treatment-emergent Adverse Events by System Organ Class and MedDRA Preferred Term and Severity (Randomized Safety Sample)
- CT-8.4 Incidence of Deaths Due to Treatment-Emergent Adverse Events by System Organ Class and MedDRA Preferred Term (Randomized Safety Sample)
- CT-8.5.1 Incidence and Occurrence (Number of Events) of Serious Treatment-Emergent Adverse Events by System Organ Class and MedDRA Preferred Term (Randomized Safety Sample)
- CT-8.5.2 Incidence of Serious Treatment-emergent Adverse Events by System Organ Class and MedDRA Preferred Term and Severity (Randomized Safety Sample)
- CT-8.6.1 Incidence of Treatment-Emergent Adverse Events Resulting in Discontinuation from Trial by System Organ Class and MedDRA Preferred Term (Randomized Safety Sample)

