- CT-8.6.2 Incidence of Treatment-Emergent Adverse Events Resulting in Discontinuation from Trial by System Organ Class, MedDRA Preferred Term and Severity (Randomized Safety Sample)
- CT-9.1 Listing of Deaths (Safety Sample)
- CT-9.2 Listing of Serious Adverse Events (Safety Sample)
- CT-9.3 Listing of Discontinuations of Study Medication Due to Adverse Events(Safety Sample)
- CT-10.1.1 Laboratory Test Results for Serum Chemistry - Mean Change from Baseline (Randomized Safety Sample)
- CT-10.1.2 Laboratory Test Results for Hematology - Mean Change from Baseline (Randomized Safety Sample)
- CT-10.1.3 Laboratory Test Results for Urinalysis - Mean Change from Baseline (Randomized Safety Sample)
- CT-10.1.4 Laboratory Test Results for Other Clinical Laboratory Tests - Mean Change from Baseline (Randomized Safety Sample)
- CT-10.2 Incidence of Laboratory Values of Potential Clinical Relevance (Randomized Safety Sample)
- CT-10.3.1 Listing of Laboratory Values of Potentially Clinical Relevance by Subject(Safety Sample)
- CT-10.3.2 Listing of Laboratory Values of Potentially Clinical Relevance by Type (Safety Sample)
- CT-10.3.3 Criteria for Laboratory Values of Potentially Clinical Relevance
- CT-10.4 Listing of Potentially Liver Injury Related Laboratory Test Abnormalities by Subject (Safety Sample)
- CT-11.1.1 Vital Sign Parameters - Mean Change from Baseline (Randomized Safety Sample)
- CT-11.1.2 Mean Change from Baseline in Weight, Height, BMI and Waist Circumference (Randomized Safety Sample)
- CT-11.2 Incidence of Vital Signs of Potential Clinical Relevance (Randomized Safety Sample)
- CT-11.3.1 Listing of Vital Signs of Potentially Clinical Relevance by Subject(Safety Sample)
- CT-11.3.2 Criteria for Potentially Clinically Relevant Vital Sign Abnormalities
- CT-12.1 ECG Parameters - Mean Change from Baseline (Randomized Safety Sample)
- CT-12.2 Incidence of ECG Measurements of Potential Clinical Relevance (Randomized Safety Sample)
- CT-12.3.1 Listing of ECG Measurements of Potentially Clinical Relevance (Safety Sample)
- CT-12.3.2 Criteria for ECG Measurements of Potentially Clinical Relevance
- CT-13.1.1 Simpson-Angus Scale Total Score - Mean Change from Baseline by Week - OC (Open-Label Safety Sample)
- CT-13.1.2 Barnes Akathisia Rating Scale Global Score - Mean Change from Baseline by Week - OC (Open-Label Safety Sample)
- CT-13.1.3 AIMS Movement Rating Score - Mean Change from Baseline by Week - OC (Open-Label Safety Sample)

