- CT-13.2.1 Columbia-Suicide Severity Rating Scale (C-SSRS) (children's version) - Suicidality (Open-Label Safety Sample)

- CT-13.2.2 Columbia-Suicide Severity Rating Scale (C-SSRS) (children's version) by Type (Open-Label Safety Sample)
- CT-14 Extent of Exposure to Investigational Medicinal Products in Open-Label Stabilization Phase (Open-Label Safety Sample)
- CT-15.1 Adverse Events (All Causalities) (Open-Label Safety Sample)
- CT-15.2.1 Incidence and Occurrence of Treatment-Emergent Adverse Events by System Organ Class and MedDRA Preferred Term (Open-Label Safety Sample)
- CT-15.2.2 Incidence of Treatment-Emergent Adverse Events by System Organ Class, MedDRA Preferred Term and Severity (Open-Label Safety Sample)
- CT-15.3.1 Incidence and Occurrence (Number of Events) of Potentially Drug-Related Treatment-Emergent Adverse Events by System Organ Class and MedDRA Preferred (Open-Label Safety Sample)
- CT-15.3.2 Incidence of Potentially Drug-Related Treatment-Emergent Adverse Events by System Organ Class, MedDRA Preferred Term and Severity (Open-Label Safety Sample)
- CT-15.4 Incidence of Deaths Due to Treatment-Emergent Adverse Events by System Organ Class and MedDRA Preferred Term (Open-Label Safety Sample)
- CT-15.5.1 Incidence and Occurrence (Number of Events) of Serious Treatment-Emergent Adverse Events by System Organ Class and MedDRA Preferred Term (Open-Label Safety Sample)
- CT-15.5.2 Incidence of Serious Treatment-Emergent Adverse Events by System Organ Class, MedDRA Preferred Term and Severity (Open-Label Safety Sample)
- CT-15.6.1 Incidence of Treatment-Emergent Adverse Events Resulting in Discontinuation from Trial by System Organ Class and MedDRA Preferred Term (Open-Label Safety Sample)
- CT-15.6.2 Incidence of Treatment-Emergent Adverse Events Resulting in Discontinuation from Trial by System Organ Class, MedDRA Preferred Term and Severity (Open-Label Safety Sample)
- CT-15.7 Incidence and Occurrence (Number of Events) of Non-Serious Treatment-Emergent Adverse Events by System Organ Class and MedDRA Preferred Term (Open-Label Safety Sample)
- CT-16.1.1 Laboratory Test Results for Serum Chemistry - Mean Change from Baseline (Open-Label Safety Sample)
- CT-16.1.2 Laboratory Test Results for Hematology - Mean Change from Baseline (Open-Label Safety Sample)
- CT-16.1.3 Laboratory Test Results for Urinalysis - Mean Change from Baseline (Open-Label Safety Sample)

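### Four SAP tables count TEAEs that led to leaving the trial, where the protocol asks for TEAEs that led to stopping the IMP; the change is undeclared and could understate AE-related drug stopping

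*SAP*

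**What the plan says.** **Protocol.** Section 7.6.1.2 includes "TEAEs leading to discontinuation of the IMP" among the AE incidences for the Randomized Safety Sample. Section 7.6.1.1 has the same item for the Open-label Safety Sample.

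**SAP tables (Appendix 4).**
- CT-8.6.1, an incidence table: "Treatment-Emergent Adverse Events Resulting in Discontinuation from Trial by System Organ Class and MedDRA Preferred Term (Randomized Safety Sample".
- CT-8.6.2, the severity breakdown: "Treatment-Emergent Adverse Events Resulting in Discontinuation from Trial by System Organ Class, MedDRA Preferred Term and Severity (Randomized Safety Sample".
- CT-15.6.1: "Incidence of Treatment-Emergent Adverse Events Resulting in Discontinuation from Trial by System Organ Class and MedDRA Preferred Term (Open-Label Safety Sample".
- CT-15.6.2 is the open-label severity breakdown on the same basis.

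**SAP 9.2 and its listing.** The incidence bullet names discontinuations caused by TEAEs without saying whether drug or trial is meant. The closing sentence of 9.2 does say: "Deaths, SAEs, and AEs leading to discontinuation from the trial will be listed for the safety samples". The listing planned in Appendix 4, CT-9.3, is instead a "Listing of Discontinuations of Study Medication Due to Adverse Events".

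**SAP Section 14.** The declared changes are the dropped interim analysis and the move to descriptive efficacy summaries. Nothing is said about the AE discontinuation summary.

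**The concern.** Stopping the drug and leaving the trial are separate events under this protocol, so a table built on one need not match a table built on the other. Safety and tolerability form the secondary objective, and AE-related drug stopping is a direct summary of tolerability. With the analysis now descriptive, readers will compare simple percentages across three small arms, where one subject matters. The protocol's measure is also the one that Protocol 1.2.2 reports for the 52-week extension trial (Trial 31-12-294), so changing the event weakens that comparison.

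**Working it through.** The documents give no rate for AE-related discontinuation, so there is no plan figure to reproduce. The check is a comparison of text, followed by simple arithmetic on what one subject is worth.

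**Step 1. Which event each place uses.**

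| Place | Event |
|---|---|
| Protocol 7.6.1.1, 7.6.1.2 | stopping IMP |
| SAP 9.2, incidence bullet | not specified |
| SAP 9.2, listing sentence | leaving the trial |
| SAP CT-8.6.1, CT-8.6.2, CT-15.6.1, CT-15.6.2 | leaving the trial |
| SAP CT-9.3 | stopping study medication |
| SAP Section 14 | no change declared |

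No SAP table is titled for the incidence the protocol requires. The 9.2 listing sentence and CT-9.3 describe the same listing by different events.

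**Step 2. Whether the two events can come apart.** Protocol 3.8.3.4 says: "A subject may initially express their desire to interrupt or discontinue IMP administration, which is not equivalent to a complete withdrawal of consent". It also asks that subjects who have not fully withdrawn be followed through the planned assessments where possible. Protocol 3.10 makes a subject a completer by attendance at double-blind Week 12, whether or not all IMP was taken. They can therefore differ.

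**Step 3. Who could be omitted if the tables are programmed as titled.**
- *(a) Double-blind phase, stays to Week 12.* A subject stops IMP for a TEAE, keeps attending and completes Week 12. Under 3.10 this subject did not discontinue the trial, so is not counted in CT-8.6.1 or CT-8.6.2.
- *(b) Either phase, exit coded otherwise.* A subject stops IMP for a TEAE and the trial exit is recorded under another reason. Protocol 3.8.3.3 lists withdrawn consent separately from the AE-related reasons. A filter on trial exit due to AE would miss this subject.
- *Not omitted on this ground.* A subject who stops IMP and has only the 30-day safety contact. Under 3.10 post-treatment contacts do not count as the last scheduled visit, so this subject has discontinued the trial.
- *Route (a) does not arise in the open-label phase.* Protocol 3.2.1 requires 12 weeks on a stable dose before randomization, and 3.7.1.6.2 discontinues subjects who have not met the stability criteria by Week 20. A subject who permanently stops drug therefore leaves the trial. Only route (b) applies to CT-15.6.1 and CT-15.6.2.

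**Step 4. Direction.** Assume that anyone who leaves the trial because of a TEAE also stops IMP because of it. Then the trial-exit count is a subset of the IMP-stop count, and the titled tables can only equal or fall below the protocol's figure.

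**Step 5. What one subject is worth.** Change in rate per omitted subject = 1/n.
- Planned double-blind arm, n = 38: 1/38 = 2.6 percentage points.
- Planned open-label sample, n = 228: 1/228 = 0.4 points.
- The trial ended early, so the actual arms may be smaller. If an arm had half the planned size (assumed, n = 19): 1/19 = 5.3 points.

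**Step 6. Illustration, with assumed counts.** If 4 of 38 stopped IMP for a TEAE, the protocol's rate is 4/38 = 10.5%. With one omitted the table shows 3/38 = 7.9%; with two, 2/38 = 5.3%. For context only: Protocol 1.2.2 reports 10 extension-trial subjects with TEAEs that led to stopping IMP, and 56 subjects as 50.9%. That implies 56/0.509 = 110 subjects and a rate of 10/110 = 9.1%, over a longer exposure.

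**The case against.** The strongest reply is that this is loose terminology with little practical effect.

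- **The 9.2 incidence bullet is compatible with the protocol.** The appendix titles are only proposed, and no derivation is given. A programmer could follow the protocol under these titles. This stands: the undercount depends on programming.
- **Few subjects would stay in the trial off drug.** The double-blind schedule has no separate off-drug track, and early terminators go to the Week 12/ET procedures. This makes route (a) uncommon, but Protocol 3.8.3.4 and 3.10 still allow it.
- **Other outputs cover the cases.** CT-9.3 lists AE-related stops of study medication. DREAS-2 lists AEs among subjects who left through withdrawn consent. The events remain in the general TEAE tables. This stands as regards the information, but a listing does not give an incidence by treatment group, which is what the protocol asks for.

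A reader might infer that any child who stops drug but stays in follow-up is lost from the table. Protocol 3.10 does not support that for a child seen only at the 30-day safety contact. A reader might also infer that good retention would generally look like good tolerability. Retention could hide a subject only through route (a), in the double-blind phase, and the documents do not show how often that would happen.

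**Conclusion.** The mismatch is real, undeclared and compounded by the SAP's internal inconsistency. It should be corrected. Its effect is conditional: it arises only if the tables are programmed as titled and only for subjects in routes (a) or (b). The undercount may be zero and cannot be sized, because the documents give neither a rate of stopping IMP for a TEAE nor a rate of staying on off drug. The direction rests on the assumption that leaving the trial for a TEAE entails stopping IMP for it, and the 2.6-point figure rests on the planned arm size. The documents do not support saying that the main tolerability evidence is lost. No table is designated as such, and the affected subjects should still be traceable in other outputs.

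**What to change.** Define and title CT-8.6.1, CT-8.6.2, CT-15.6.1 and CT-15.6.2 as TEAEs leading to permanent discontinuation of the IMP. State in SAP 9.2 how this is derived from the AE data. Reword the 9.2 incidence bullet and listing sentence so that both agree with the protocol and CT-9.3. Leave AE-related trial exit to the existing reasons-for-discontinuation tables, CT-2.1 and CT-2.2. If the sponsor wants trial exit in the AE tables as well, Section 14 should say so and the protocol's summary should still be produced.

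The cost is SAP wording and a filter change in four tables, with possibly a slightly less favourable tolerability figure. The documents do not describe the AE form, so a field recording that IMP was stopped because of the AE is an assumption. However, the TEAE definition in SAP 9.2 already needs to know whether an AE led to stopping study medication.
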